4. STATISTICAL METHODS

4.1 General Methodology

Data will be analyzed by Emanate biostatistics personnel. Dataset specifications will be in conformance with the FDA guideline *Submitting Study Datasets for Vaccines to the Office of Vaccines Research and Review* (2019). Statistical analyses will be reported with tables, figures, and listings, presented in rich text format, and using recommended ICH numbering. Output specifications for all tables, figures, and listings will be in conformance with guidelines specified by the ICH in Appendix 7 of the Electronic Common Technical Document Specification (Apr 2003).

4.1.1 Reporting Conventions

Participants in Cohort A and Cohort B will be analyzed independently for the final analysis, with distinct sets of tables, figures, and listings provided for each cohort.

For Cohort A, tables and figures will be summarized by sub-cohort (Sub-cohort A1 and Sub-cohort A2) and study vaccine group. Tables summarizing demographics and other baseline characteristics will also include columns for all participants combined within each sub-cohort. For Cohort B, tables and figures for each cohort will be summarized by study vaccine group. Tables summarizing demographics and other baseline characteristics will also include a column for all participants combined.

In general, all data collected and any derived data will be presented in participant data listings, for all enrolled participants. Listings will be ordered by site, participant number, cohort sub-group (Cohort A only), study vaccine group, and assessment or event date. The study vaccine group presented in listings will be based on the planned assignment, unless otherwise noted.

In general, continuous variables will be summarized to indicate the study population sample size (N), number of participants with available data (n), mean, SD, median, first (Q1) and third (Q3) quartiles, minimum, and maximum values. Categorical variables will be summarized by the population size (N), number of participants with available data (n), number of participants in each category, and the percentage of participants in each category. Unless otherwise noted, the denominator to determine the percentage of participants in each category will be based on the number of participants with available data. Select ordinal data may be summarized using both descriptive statistics and counts and percentages of participants in each category, as appropriate.

In general, non-zero percentages will be rounded to one decimal place, with the exception of “100%” which will be displayed without any decimal places. Select immunogenicity parameters will be rounded to additional decimal places, if warranted by the nature of data collection. When categorical data are presented, the percentages will be suppressed when the frequency count is equal to zero. Rounding conventions for presentation of summary statistics will be based on the precision of the variable of summarization, as it is collected in its rawest form (i.e., on the electronic case report form [eCRF] or as provided within an external file) and are outlined as follows:

- The mean and median will be rounded to one more decimal place than the precision of the variable of summarization;
- Measures of variability (e.g., SD, SE) will be rounded to two more decimal places than the precision of the variable of summarization; and
- Minimum and maximum values will be presented using the same precision as the variable of summarization.

Other statistics (e.g., CIs) will be presented using the same general rules outlined above, or assessed for the most appropriate presentation based on the underlying data.

No formal statistical analysis will be performed to compare study vaccine groups. This study is exploratory in nature; descriptive statistics will be tabulated by cohort and study vaccine group and reviewed to evaluate all study endpoints.

4.1.2 *Summarization by Visit*

Data summarized by study visit will be based on the nominal, scheduled visit label as reported on the eCRF. Data collected for the last participant visit completed will be summarized separately for:

- The scheduled Final Visit (defined as 365 days after the last study vaccine dose) for those participants who complete the scheduled end of study visit, per protocol; and
- The last visit completed on-study, combining data collected for participants who complete the Final Visit as well as the early termination visit for those participants who discontinue the study early. This summary will be labelled as “Final Visit / Early Termination” in the analysis.

Data collected at unscheduled visits will not be included in by-visit summaries, but will be considered when endpoint derivations potentially include multiple visits (e.g., determination of baseline value, determination of worst post-baseline value, etc.). All data will be included in participant listings.

4.1.3 *Data Handling Rules*

Unless otherwise noted (e.g. immunogenicity data handling rules), values reported as greater than or less than some quantifiable limit (e.g., “< 1.0”) will be summarized with the sign suppressed in summary tables and figures, using the numeric value reported. Data will display on participant listings to include the sign.

4.1.4 *Standard Calculations*

Where appropriate, the calculated study day of each assessment or event will be presented with the assessment or event date on participant data listings, where study day will be determined as:

- The assessment/event date minus the date of first dose of study vaccine, if the assessment/event date is prior to the date of first dose of study vaccine; and
- The assessment/event date minus the date of first dose of study vaccine, plus one, if the assessment/event date is on or after the date of first dose of study vaccine.

Other variables requiring calculations will be derived using the following formulas:

- **Days:** A duration between two dates expressed in days will be calculated using the following conventions:
 - Later date – earlier date + 1, if the earlier date is on or after the date of first dose of study vaccine; or

- Later date – earlier date, if the earlier date is prior to the date of first dose of study vaccine.
- **Months:** A duration expressed in months will be calculated by dividing the duration in days by (365.25 / 12).
- **Years:** A duration expressed in years will be calculated by dividing the duration in days by 365.25.
- **Change from Baseline:** Change from baseline will be calculated as the post baseline value minus the baseline value.
- **Percentage Change from Baseline:** Percentage change from baseline will be calculated as the change from baseline divided by the baseline value, multiplied by 100.
- **GMC/GMT:** Calculated as the anti- $\log_{10}(\text{mean}[\log_{10}X_i])$, where X_i is the assay concentration/titer result for participant i .
- **GMFR:** Calculated as the anti- $\log_{10}(\text{mean}[\log_{10}Y_i/B_i])$, where Y_i is the post dose assay result for participant i ; and B_i is the baseline assay result for participant i .
- **Seroconversion (Cohort A):** Proportion of participants achieving ≥ 4 -fold rise from before vaccination to each subsequent time point evaluated after vaccination.
- **Seroresponse (Cohort B):** Proportion of participants achieving ≥ 4 -fold rise from before vaccination to each subsequent time point evaluated after vaccination.

4.2 Analysis Sets

The analysis sets are defined as follows:

- **Full Analysis Set (FAS):** the FAS includes all randomized participants. Assignment of participants to study vaccine group is based on the planned assignment.
- **Immunogenicity Analysis Set (IAS):** The IAS includes all randomized enrolled participants who meet the following criteria:
 - Receive the specified number of doses of the study vaccine to which they are randomly assigned, within the predefined window;
 - Have at least one valid and evaluable immunogenicity result after the specified study vaccine dose;
 - Have blood collection within an appropriate window after the specified dose; and

- Have no other major protocol deviations as determined by the Arcturus Therapeutics Medical Monitor that would require exclusion from the immunogenicity analysis set.
- Safety Set (SS): The SS includes all randomized participants who receive at least one dose of the study vaccine. Assignment of participants to study vaccine group is based on the study vaccine actually received.
- Modified Intent to Treat Analysis Set (mITT): The mITT set includes all eligible randomized participants who receive all protocol-required doses of study vaccine up to the evaluation timepoint concerned. This set excludes any participant that receives an off-study COVID-19 vaccine prior to the analysis timepoint. Assignment of participants to study vaccine group is based on the planned study vaccine assignment.

Data summaries to be presented on more than one analysis set will only be produced on both analysis sets if there is a difference in the analysis sets.

4.3 Study Participants

4.3.1 Disposition of Participants

Participant disposition will be summarized for the SS by study vaccine group and over all participants combined for each cohort (sub-cohorts for Cohort A). Summaries will include the number and percentage of participants in each analysis set, completing the study, and discontinuing the study early by the primary reason for discontinuation.

The number and percentage of screen failures will be presented by screen failure reason, based on the total number of participants screened.

4.3.2 Protocol Deviations

Major protocol deviations for each cohort will be summarized by study vaccine group and over all participants combined for each cohort (sub-cohorts for Cohort A) for the SS. Major protocol deviations are protocol deviations captured on-study that are deemed by Arcturus to potentially impact the immunogenicity or safety conclusions of the study.

All major protocol deviations will be determined and appropriately categorized prior to database lock and prior to breaking the blind of the study vaccine group assignments. The number and percentage of participants with any major protocol deviations as well as the number and percentage of participants with deviations within each category will be presented. Protocol deviations will also be presented in data listings by cohort, participant and study vaccine group.

4.4 Demographic and Other Baseline Characteristics

Demographic variables including age, gender, preferred arm (left-handed or right-handed), ethnicity and race will be summarized by study vaccine group and over all participants combined for each cohort (sub-cohorts for Cohort A) for the IAS and SS.

Age will be summarized as collected on the eCRF using descriptive statistics. Gender, preferred arm, ethnicity, and race will be summarized with the number and percentage of participants in each parameter category.

Baseline characteristics include medical history, height, weight, and body mass index (BMI). Baseline characteristics will be summarized as provided on the eCRF for the IAS and SS by study vaccine group, and over all participants combined, for each cohort. Height, weight, and BMI at baseline will be summarized using descriptive statistics. Frequency counts and percentages to summarize participants reporting abnormal medical history by body system will be presented.

4.5 Immunogenicity Evaluation

4.5.1 Datasets Analyzed

All immunogenicity summaries will be based on the IAS and summaries for key selected assays may be repeated for the FAS. For participants who have a confirmed COVID infection on-study, data will be censored at the last visit prior to their confirmed COVID infection.

A data listing of participants excluded from the IAS, to include the reason for exclusion, will be presented.

4.5.2 Primary Immunogenicity Endpoint Analysis Methods

Immunogenicity endpoints as described in [Section 3.4.1.1](#) will be summarized by study vaccine group and visit using descriptive statistics for each cohort.

The number and percentage of participants with non-missing titers will be presented for each visit. Geometric mean concentrations and GMFRs will be summarized and presented, along with corresponding 95% student t CIs. The proportion of participants achieving a ≥ 4 -fold rise (seroconversion for Cohort A or seroresponse for Cohort B) from before vaccination to each subsequent time point evaluated after vaccination will also be presented, along with corresponding 95% Clopper-Pearson exact CIs.

For the D614G MNT assay, results may be presented in IU/mL in addition to AU/mL with a conversion of 1 IU/mL = 1.275 AU/mL. For GMC calculations, antibody titers below the lower limit of quantification (LLOQ) will be set to half that LLOQ value for the purposes of analysis. For seroconversion (Cohort A) and seroresponse (Cohort B), LLOQ values will be set to the LLOQ value. Missing values will be excluded from analysis.

Box and whisker plots will be generated to display the distribution of titers separately for each study vaccine group and antigen, for both baseline and post-baseline time points. Additional graphical representations of immunogenicity data, including (but not limited to) reverse cumulative frequency plots, may also be provided.

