3. INVESTIGATIONAL PLAN

3.1 Overall Study Design

This is a randomized, observer-blind, two-cohort study evaluating the safety, reactogenicity, and immunogenicity of three investigational SARS-CoV-2 self-amplifying RNA vaccines. This study is intended for execution in one or more clinical study sites in one or more of the following countries – Singapore, South Africa and the United States (US).

The study will initially enroll approximately 72 adult participants divided into two cohorts of 36 adult participants based on previous vaccination status against SARS-CoV-2.

Cohort A will include a total of 36 adult participants ≥ 21 to ≤ 65 years of age who have not been previously vaccinated (vaccine-naïve) with a SARS-CoV-2 vaccine. Cohort A is further subdivided into two vaccine-naïve sub-cohorts. Participants in Sub-cohort A1 (n=12 participants, seronegative) will be randomly assigned (1:1:1) to receive two 5- μ g doses of ARCT-165, ARCT-154, or ARCT-021. Participants in Sub-cohort A2 (n=24 participants, seropositive) will be randomly assigned (3:1) to receive two 5- μ g doses of ARCT-154 or ARCT-021 respectively. Participants in both sub-cohorts will receive the first dose on Day 1 and the second dose on Day 29.

Cohort B will include a total of 36 adult participants ≥ 21 to ≤ 65 years of age who have been previously vaccinated (5 months or longer prior to study enrollment) with the BNT162b2 (Comirnaty) SARS-CoV-2 vaccine. Participants will be randomly assigned (1:1:1) to receive one 5- μ g dose of ARCT-165, ARCT-154, or ARCT-021. Study vaccine will be given as a single dose on Day 1.

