3.4 Immunogenicity, Safety, and Other Variables

3.4.1 Immunogenicity Variables

3.4.1.1 Primary Immunogenicity Variables

The primary immunogenicity endpoints include:

- SARS-CoV-2 neutralizing antibody titer by pseudoviral microneutralization assay (ancestral strain, D614G variant, and B.1.351 [Beta] variant [as available]) from the PPD Laboratory. Assay results will be evaluated as follows:
 - Geometric mean concentrations (GMCs) at each time point designated in the schedule of assessments;
 - Geometric mean fold rise (GMFR) from baseline (pre-vaccination blood samples drawn Day 1) to each subsequent time point evaluated after vaccination;
 - Proportion of participants achieving ≥ 4 -fold rise in titer from baseline (pre-vaccination blood samples drawn Day 1) to each subsequent time point evaluated after vaccination; and
 - GMC ratio (ARCT-021/ARCT-165, ARCT-165/ARCT-154, and ARCT-021/ARCT-154 where applicable) measured at all time points evaluated.

- Binding antibody titer: Immunoglobulin G (IgG) to variant-specific SARS-CoV-2 full-length spike, receptor-binding domain (RBD), and N antigens measured by Meso Scale Discovery (MSD) multiplex assay from the PPD Laboratory (ancestral strain, D614G variant, and B.1.351 [Beta] variant, as available):
 - Geometric mean concentrations (GMCs) at each time point designated in the schedule of assessments;
 - GMFR from baseline (pre-vaccination blood samples drawn Day 1) to each subsequent time point evaluated after vaccination; and
 - Proportion of participants achieving ≥ 4 -fold rise in GMC from baseline (pre-vaccination blood samples drawn Day 1) to each subsequent time point evaluated after vaccination.

3.4.1.2 *Exploratory Immunogenicity Variables*

The cell-mediated immune responses to different variants of SARS-CoV-2 following vaccination is an exploratory immunogenicity endpoint. It will be measured at designated time points using one or more of the following assays:

- ELISpot (Oxford Immunotec T-spot) assay assessing IFN- γ secreting T cells (spots/ 10^6 PBMCs);
- Intracellular Cytokine Staining (ICS) assay assessing IFN- γ , TNF- α , IL-2, IL-4, IL-5, and IL-13 expressing CD4+ and CD8+ T cells; or
- Fc effector function: Antibody-mediated cytotoxicity will be measured using surrogate assays measuring CD16 signaling at some or all time points designated in the schedule of assessments.

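### SAP 4.5.2 gives a zero-width 95% CI to any antibody GMC whose values are all below LLOQ, and has no rule for marking that interval not estimable

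*SAP*

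**What the plan says.** SAP 4.5.2 (Primary Immunogenicity Endpoint Analysis Methods) makes three statements that matter here.

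- Interval method: "Geometric mean concentrations and GMFRs will be summarized and presented, along with corresponding 95% student t CIs".
- Substitution for GMC: "antibody titers below the lower limit of quantification (LLOQ) will be set to half that LLOQ value for the purposes of analysis". The sentence is restricted to GMC calculations.
- Substitution for the proportion with a ≥4-fold rise: "For seroconversion (Cohort A) and seroresponse (Cohort B), LLOQ values will be set to the LLOQ value". That proportion gets a Clopper-Pearson interval, not a t interval.

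No substitution value is stated for GMFR. SAP 4.1.3 has a general default (use the reported number without its sign), but it excepts immunogenicity data handling rules.

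SAP 4.1.4 (Standard Calculations) defines the GMC as the antilog of the mean log10 result and the GMFR as the same operation on individual ratios to baseline. SAP 3.4.1.1 lists among the primary variables "Geometric mean concentrations (GMCs) at each time point designated in the schedule of assessments", and protocol Appendix 1 draws antibody blood at both vaccination visits, including Day 1. Section 4.5.2 tabulates the number of non-missing titres, but not the number below LLOQ.

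**The concern.** Half-LLOQ substitution gives every unquantifiable sample the same number. A t interval takes its width from the spread of the values, so a cell made up only of substituted constants has no spread and the interval collapses to a point. In print, that looks like perfect precision where nothing was quantified.

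Such cells are foreseeable. Sub-cohort A1 is vaccine-naive and described as seronegative, and 12 participants randomised 1:1:1 give 4 per vaccine. N-antigen IgG is one of the primary binding endpoints, while the vaccines encode spike only (SAP 3.3.1), so N-IgG in A1 could stay low after vaccination too.

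Describing antibody responses is a primary objective and no formal group comparison is planned, so the GMCs, GMFRs and their intervals are a main result. A reader could take a GMFR of 1.0 (1.0 to 1.0) as firm evidence of no response.

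**Working it through.** The documents state no sample size calculation, interval width, LLOQ or SD, so there is no planned figure to reproduce.

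**Inputs from the documents.** 95% t interval on the log10 scale; LLOQ/2 substitution for GMC; group sizes 12/3 = 4 (A1), 18 and 6 (A2, 24 split 3:1), 36/3 = 12 (Cohort B).

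**Inputs assumed.** Log-normal titres, log10 SD 0.2 to 0.8, and 25%, 50%, 75% or 90% of the distribution below LLOQ.

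**1. All values below LLOQ (exact).** The interval is mean ± t(0.975, n−1) × s/√n. Every value equals log10(LLOQ/2), so s = 0 and both limits equal LLOQ/2. This holds for n = 4, 6, 12 and 18.

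**2. GMFR.** If all values are below LLOQ at baseline and at the later visit, and the same constant is used at both, every ratio is 1. The result is 1.0 (1.0 to 1.0) with LLOQ or with LLOQ/2. The choice does matter where only the baseline is below LLOQ: Y/(LLOQ/2) = 2 × Y/LLOQ, so the fold rise doubles under LLOQ/2.

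**3. What the data support.** With 0 of 4 quantifiable, the Clopper-Pearson upper limit is 1 − 0.025^(1/4) = 60.2%. For 0/6, 0/12 and 0/18 it is 45.9%, 26.5% and 18.5%.

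**4. Chance that a whole group is below LLOQ, p^n.**

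| True share below LLOQ | n=4 | n=6 | n=12 | n=18 |
|---|---|---|---|---|
| 75% | 32% | 18% | 3% | 0.6% |
| 90% | 66% | 53% | 28% | 15% |

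**5. Substituted t interval against the interval on uncensored values** (simulation; ranges over the four group sizes and the assumed SDs).

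| True share below LLOQ | Mean width ratio | Coverage of the true geometric mean |
|---|---|---|
| 25% | 0.90 to 1.31 | 91% to 95% |
| 50% | 0.70 to 1.26 | 79% to 95% |
| 75% | 0.40 to 0.93 | 0% to 94% |
| 90% | 0.17 to 0.55 | 0% to 85% |

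At 50% below, the interval is wider than the uncensored one at SD 0.2 and about equal at SD 0.3. At 75% below and SD 0.4, the width ratio is 0.54 to 0.62 and coverage 68% to 84%. Much of the loss is bias of the substituted mean. At SD 0.4 it is +0.10 log10 at 75% below (10^0.10 = 1.26-fold) and +0.26 at 90% (10^0.26 = 1.8-fold).

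**6. Separating the zero-width samples at n=4** (SD 0.3 to 0.6). Overall coverage at 50%, 75% and 90% below is about 91%, 66–68% and 4–34%. Among partly censored samples alone it is 97–100% at both 50% and 75%. The 75% figure is almost all zero-width samples: (1 − 0.316) × (0.97 to 1.00) = 0.66 to 0.68. At 90% below, partly censored samples cover 99% at SD 0.3, but 39% at SD 0.45 and 12% at SD 0.6.

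**7. A partly censored cell of four can be wide.** Take three values at LLOQ/2 and one at 4 × LLOQ. In LLOQ units the mean log is (3 × (−0.301) + 0.602)/4 = −0.075, s = 0.452, and the half-width is 3.182 × 0.452/2 = 0.718. The GMC is 0.84 (0.16 to 4.40) × LLOQ.

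**The case against.** The strongest reply is that the harm is limited and partly offset elsewhere in the plan. The study is descriptive, and no test, decision rule or sample size uses these intervals. Section 4.5.2 also reports the ≥4-fold-rise proportion with an exact interval, so a non-responding group of four would show 0/4 (0% to 60%) in the same output. Box plots are planned at baseline and afterwards, and listings keep the < sign (SAP 4.1.3). All of this stands and limits the damage, but none of it corrects the tabulated GMC or GMFR interval, and no table counts the values below LLOQ.

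It is also fair that seronegative in A1 means nucleocapsid-negative, tested at screening only in South Africa and the US (protocol exclusion 19, Appendix 3). It is not a spike or neutralisation result below LLOQ. All-below cells at A1 baseline are therefore plausible, not documented.

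A reader might infer that half-LLOQ substitution makes the intervals of heavily censored groups far too narrow in general, or that the t interval should be withheld once more than half the values are below LLOQ. Steps 5 and 6 do not support either reading. At about half below LLOQ the width is often similar or greater, and a more-than-half rule would delete intervals with adequate coverage, such as partly censored groups of four at 75% below. The worst figures for groups of 12 (coverage 3% at 75% below and SD 0.6, against 92% at SD 0.3) need assumptions the documents do not supply. Groups of that size are in Cohort B, whose participants had two BNT162b2 doses.

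**Conclusion.** The point holds for cells entirely below LLOQ. The zero-width GMC interval follows algebraically from the stated rules and needs no assumption about the assay. The GMFR result needs all values below LLOQ at both visits and one constant throughout. How often such cells will occur is unknown; A1 at Day 1, and A1 N-IgG later, are the plausible places.

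For partly censored cells only a conditional statement is justified. Depending on the SD and group size, the interval can be much too narrow and off-centre once about three quarters or more of values are below LLOQ, with much of the coverage loss coming from bias. That rests on assumed log-normality, SDs and censoring shares.

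The consequence is misreported precision on a primary descriptive endpoint, not a wrong decision. It is still worth correcting, because the rule as written prints an error bar that is wrong on its face.

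**What to change.** Amend SAP 4.5.2 as follows.

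1. Tabulate n (%) below LLOQ in every group-by-visit cell, beside the count of non-missing titres.
2. When all values in a cell are below LLOQ, report the GMC as `<LLOQ` and its CI as not estimable. Mark the GMFR CI not estimable when all values at both visits are below LLOQ.
3. State which value replaces below-LLOQ results in the GMFR.

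No suppression threshold is needed for partly censored cells. A left-censored normal likelihood interval may be added as an optional sensitivity analysis for heavily censored cells. In simulation it covered 93% to 96% (n = 12 and 18, SD 0.3 to 0.6, 50% and 75% below LLOQ, at least two quantified values). It was not checked at n = 4.

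The cost is a few sentences and some extra table rows. All-below-LLOQ cells lose an interval that carried no information. SAP section 1 already allows amendment for Cohort A, which contains A1, before database lock.
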